### Prohibited Medication and Procedures

Patients are required to discontinue all non-study-permitted pain medication (oral or topical) starting at the screening visit until after completion of the week-24 study visit. Concomitant medications that contain NSAIDs are prohibited from the screening visit until after completion of the week-24 study visit. This applies even if a patient discontinues study drug prematurely but remains in the study to participate in the remaining study visits. The only exception is aspirin/5-aminosalicylic acid, which is permitted for cardiac prophylaxis. Opioid analgesic medications (including tramadol) are prohibited starting at least 4 weeks prior to the screening visit until the end of the follow-up period with no exceptions.

Other excluded medications/procedures starting at the screening period include:

- Any other investigational agent
- Medical or regular recreational use of marijuana
- Chondroitin sulfate
- Glucosamine
- Hyaluronic Acid Intra-articular infusions
- Anticoagulants and antiplatelets (eg, warfarin, heparins, factor Xa inhibitors, thrombin inhibitors, aspirin >150 mg daily, clopidogrel)
- Muscle relaxants including cyclobenzaprine, carisoprodol, orphenadrine, tizanidine (see Section 7.7.2 in the protocol for permitted muscle relaxants)
- Corticosteroids (topical, intranasal, and inhaled formulations are permitted), adrenocorticotrophic hormone
- Cyclosporine, methotrexate, mycophenolate mofetil, tacrolimus (topical tacrolimus allowed)
- Azathioprine, sulfasalazine, hydroxychloroquine
- IL-6 or IL-6 receptor antagonists
- Abatacept, ustekinumab
- Tumor necrosis factor antagonists
- IL-1 inhibitors, including diacerein
- PDE-4 and Jak-kinase inhibitors
- Genicular nerve block and any other similar procedures (prohibited from within 3 months of the screening visit and up to the last study site visit in the follow-up period)

The list of concomitant medications taken by study patients is reviewed by the study team to determine if any medication falls under one of the above categories. If a concomitant medication is adjudicated to be prohibited, a protocol deviation is recorded.

The following variables are to be summarized for prohibited medications, overall and by geographical region:

- Use of at least one prohibited medication during Pre-treatment Period, Treatment Period, and Follow-up Period.
- Use of any prohibited medications, as well as selected prohibited medications (NSAIDs, opioids and corticosteroids), by visit.
- Receiving prohibited procedures during Pre-treatment Period, Treatment Period, and Follow-up Period.

## **4.4. Efficacy Variables**

### **4.4.1. Primary Efficacy Variable**

The primary endpoint of the study is the change from baseline to week 12 in the WOMAC pain subscale score.

The WOMAC index is comprised of 24 parameters grouped 3 in subscales (pain, physical function, and stiffness) and is reported using a Numerical Rating Scale score of 1-10.

### **4.4.2. Secondary Efficacy Variables**

The secondary efficacy endpoints of the study are:

- Change from baseline to week 12 in the WOMAC physical function subscale score
- Change from baseline to week 12 in the Patient Global Assessment (PGA) score
- Change from baseline to week 12 in WOMAC stiffness subscale score
- Change from baseline to week 12 in the WOMAC total score (based on the full survey)
- Percentage of patients who had a response at week 12, with response defined as an improvement by  $\geq 30\%$  in the WOMAC pain subscale scores

The Patient Global Assessment of OA (PGA) is a patient-rated assessment of current disease state on a 5-point Likert scale (1 = very good; 2 = good; 3 = fair; 4 = poor; and 5 = very poor).

#### **4.4.2.1. Supportive variables**

The following two supportive endpoints are to be analyzed instead of the exploratory area under the curve endpoint:

- WOMAC pain subscale scores averaged across Weeks 4, 8, and 12.
- WOMAC pain subscale scores averaged across Weeks 8 and 12.

#### **4.4.3. Exploratory Efficacy Variables**

The exploratory efficacy endpoints of the study are:

- The exploratory endpoint described in the protocols as “Area under the curve for WOMAC pain subscale score (for the 12-week treatment period)” is being replaced by supportive endpoints described in section 4.4.2.1.
- Change in gait and functional mobility parameters recorded by a wearable insole device from baseline to week 12 in a subset of patients at participating sites.

### **4.5. Safety Variables**

Patient safety is assessed through the collection of reported adverse events (AEs), clinical laboratory data, vital signs, ECG, neurological exams and physical exams. Unless otherwise noted, the baseline value is defined as the last available value before the first dose of study drug.

#### **4.5.1. Adverse Events and Serious Adverse Events**

Adverse event information is to be collected until the patient’s last study visit. Serious adverse event information is to be collected until the event is considered chronic and/or stable and/or resolved.

Adverse events (AE) and Serious Adverse Events (SAE) are collected from the time of informed consent signature and then at each visit until the end of follow-up visit (week 36) for AEs and until end of study visit (week 52) for SAEs. All AEs are to be coded to a “Preferred Term (PT)” and associated primary “System Organ Class (SOC)” according to the MedDRA® (the latest current available version).

An AE is any untoward medical occurrence in a patient administered a study drug which may or may not have a causal relationship with the study drug. Therefore, an AE is any unfavorable and unintended sign (including abnormal laboratory finding), symptom, or disease which is temporally associated with the use of a study drug, whether or not considered related to the study drug. An AE also includes any worsening (ie, any clinically significant change in frequency and/or intensity) of a pre-existing condition that is temporally associated with the use of the study drug. Laboratory results, vital signs, or ECG abnormalities are to be recorded as AEs if they are medically relevant: symptomatic, requiring corrective therapy, leading to treatment discontinuation and/or fulfilling a seriousness criterion.

An SAE is an AE that is classified as serious according to the criteria specified in the protocol. SAEs with an onset within 30 days of the end of the follow-up period or within 226 days of last study drug administration if the patient early terminated from the study is to be reported to the sponsor. SAEs with an onset day greater than 30 days from the end of the follow-up period/early termination visit: only fatal SAEs and those deemed by the investigator to be drug-related SAEs are to be reported to the sponsor. SAEs reported by the patient at the end-of-study phone call and deemed by the investigator to be drug-related are to be reported to the sponsor.

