### 9.4.2. Serious Adverse Events

All SAEs, regardless of assessment of causal relationship to study drug, must be reported to the sponsor (or designee) within 24 hours.

Information not available at the time of the initial report must be documented in a follow-up report. Substantiating data such as relevant hospital or medical records and diagnostic test reports may also be requested.

In the event the investigator is informed of an SAE after the patient completes the study, the following will apply:

- SAE with an onset within 30 days of the end of the follow-up period or within 226 days of last study drug administration if the patient early terminated from the study - the SAE will be reported to the sponsor. The investigator should make every effort to obtain follow-up information on the outcome until the event is considered chronic and/or stable.
- SAE with an onset day greater than 30 days from the end of the follow-up period/early termination visit - only fatal SAEs and those deemed by the investigator to be drug-related SAEs will be reported to the sponsor. The investigator should make every effort to obtain follow-up information on the outcome of a drug-related SAE until the event is considered chronic and/or stable.
- SAE reported by the patient at the end-of-study phone call and deemed by the investigator to be drug-related will be reported to the sponsor. The investigator should make every effort to obtain follow-up information on the outcome of a drug-related SAE until the event is considered chronic and/or stable.

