### 2.3. Study Plan

The study was intended to consist of a screening period of up to 30 days, followed by a 12-week randomized, double-blind, placebo-controlled treatment period, a 24-week follow-up period, and an end-of-study phone call approximately 52 weeks after the first dose of study drug (Figure 1). The purpose of the end-of-study phone call was to determine whether a patient underwent, is scheduled for, or is on a waiting list to receive joint replacement surgery, or whether joint replacement was recommended but the patient elected to defer. Thus, each patient was to be enrolled in the study for approximately 56 weeks, including the screening period and the period up to the end-of-study phone call.

As the Interim Analysis showed no treatment effect, and there were no safety signals observed, it was decided to terminate the study at the time last patient completes week 36 visit; thus, a limited number of study patients will have completed week 52 phone call.

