## 5. STATISTICAL METHODS

For continuous variables, descriptive statistics include the following: the number of patients reflected in the calculation (n), mean, median, standard deviation (SD), minimum, maximum, and the first and third quartiles (Q1 and Q3).

For categorical or ordinal data, frequencies and percentages are displayed for each category.

Unless otherwise specified, table content is to be presented sorted by descending order of frequency of system organ class for the REGN5069 1000 mg group.

**Study Observation Period** – Unless otherwise stated, analysis of all safety and non-safety variables captured at multiple visits are to be analyzed by the following observations periods:

- *The Pre-Treatment Period* is defined as the time from signing the ICF to before the first dose of study drug.
- *The Treatment Period* is defined as the days from first dose of study drug to the day of last dose + 28 days (4 weeks). Summaries for the Treatment Period are based on the SAF.
- *The Follow-Up Period* is defined from the end of the Treatment Period to the Week 36 Visit/Early Termination Visit, regardless of the patient having completed the treatment period (week 12 visit) or not.
- *The Post-Follow-Up Period* is defined from the end of the Follow-Up Period to the phone call/Early Termination Visit.

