### 5.8.1. Adverse Events

The verbatim text, the preferred term, and the primary SOC are to be listed in patient listings. Summaries that include frequencies and proportions of patients reporting AEs are to include the preferred terms and the SOCs.

**Pre-treatment AEs** are defined as AEs that developed or worsened during the Pre-Treatment Period.

**Treatment-emergent AEs (TEAEs)** are defined as AEs that developed or worsened during the Treatment Periods.

**Follow-Up AEs** are defined as AEs that developed or worsened after treatment period end (more than 4 weeks after the last dose of study drug) but before Week 36 visit.

The focus of adverse event reporting in the clinical study report is on TEAEs.

Summaries of TEAEs by treatment group, summarizing number (percentage) of patients within the specified category, during the study and by study period as applicable include:

- Overview of TEAEs, summarizing number of events,
  - Total number of TEAEs
  - Total number of Serious TEAEs
  - Patients with any TEAEs
  - Patients with any Serious TEAEs
  - Patients with any TEAEs leading to death
  - Patients with any TEAEs leading to withdrawal from study
  - Patients with any TEAEs leading to permanent study treatment discontinuation
- All TEAEs by SOC and PT
- All TEAEs by SOC, PT, severity

- All TEAEs by SOC, PT, relationship
- Study drug related TEAEs by SOC and PT
- TEAEs resulting in permanent study drug discontinuation by SOC and PT
- TEAEs leading to study drug infusion interruption by SOC and PT
- Serious TEAEs by SOC and PT
- All AEs by SOC and PT
- All AEs by severity
- All SAEs, by study period
- All SAEs by severity and study period
- All SAEs by relationship, treatment and follow-up period

Follow-up AEs will be summarized similarly as TEAEs, as well as AEs occurring during Treatment and Follow-up Periods combined.

Listing to include:

- Listing of AEs leading to death
- Listing of TEAEs leading to permanent study treatment discontinuation
- Listing of TEAEs leading to infusion interruption
- Listing of TEAEs leading to withdrawal from study
- Listing of patients with Serious TEAEs
- Listing of all joint replacements

Counts are to be provided according to treatment group and combined REGN5069 group for each PT within each primary SOC. Percentages are to be calculated based on the SAF in each treatment group and sorted by descending order of frequency of system organ class for the REGN5069 1000 mg group.

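### SAP 4.5.1 says SAEs are collected to week 52, but full recording ends at week 36 and most patients lose the week-52 call, so a post-follow-up percentage in the by-period SAE tables would not be an incidence

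*SAP*

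**What the plan says.** **Collection period.** SAP 4.5.1 states that events are collected from consent at each visit, "until the end of follow-up visit (week 36) for AEs and until end of study visit (week 52) for SAEs". Protocol 9.4.1 has the investigator record all AEs from consent to the end of the follow-up period and gives SAEs no longer recording period.

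**Reporting after follow-up.** Protocol 9.4.2 deals with SAEs that the investigator learns of after the patient has completed. SAP 4.5.1 repeats its rules:
- Full reporting applies to "SAEs with an onset within 30 days of the end of the follow-up period or within 226 days of last study drug administration", the 226-day limit being for early terminators.
- For onset more than 30 days after follow-up, "only fatal SAEs and those deemed by the investigator to be drug-related SAEs are to be reported to the sponsor". The protocol wording is the same: "only fatal SAEs and those deemed by the investigator to be drug-related SAEs will be reported to the sponsor".
- At the call, "SAEs reported by the patient at the end-of-study phone call and deemed by the investigator to be drug-related are to be reported to the sponsor".

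**The V2.0 change.** The study now ends when the last patient completes week 36. SAP 2.3 expects that "a limited number of study patients will have completed week 52 phone call", and SAP 4.5.12 says that the call will not be made for most patients. The V2.0 change table does not list 4.5.1, so its week-52 phrase stands.

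**The tables.** SAP section 5 still defines a Post-Follow-Up Period, which "is defined from the end of the Follow-Up Period to the phone call/Early Termination Visit". SAP 5.8 says that the safety observation period has four segments. V2.0 added to 5.8.1 the table "All SAEs, by study period" and a companion by severity and study period. A third new SAE table, by relationship, is limited to the treatment and follow-up periods. Percentages in 5.8.1 use the safety analysis set (SAF) of each arm.

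**The concern.** The opening of SAP 4.5.1 promises more than either document collects. A programmer who relies on it, on the four segments and on the new table titles would produce a post-follow-up row headed as all SAEs. The numerator would hold events that reached the investigator without any stated systematic enquiry, and for most of the period only fatal or drug-related ones. The denominator would be every treated patient in the arm, most of whom have no call to close the period.

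A near-empty row of that kind could be read as evidence that few serious events occur late. This matters somewhat here, because protocol 3.2.1 justifies the long follow-up by joint-safety concerns with another class of agents, and Amendment 1 added the 52-week contact on health-authority feedback. A late joint replacement with an inpatient admission could meet the seriousness criteria in protocol 9.3.2. If it began more than 30 days after follow-up, was not fatal and was judged unrelated, it would not be reportable as an SAE.

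**Working it through.** **Inputs** (nominal study days from the schedules of events): last planned dose Day 57; week-36 visit Day 253 (±7); week-52 call Day 365 (±7). From the reporting rules: 30 days after follow-up, and 226 days after last dose for early terminators.

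**1. Reproduce the documents' 226 days.** End of follow-up plus 30 days is 253 + 30 = 283. Measured from the last planned dose, 283 − 57 = 226, which matches. The two limits therefore meet at Day 283 for a patient given all three doses. Day 283 is derived, not printed; with the visit window it is 276 to 290 (246 + 30 to 260 + 30).

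**2. Nobody is under full reporting later than that.** For early terminators last dosed on Day 1 or Day 29, the 226-day limit ends at 1 + 226 = Day 227 or 29 + 226 = Day 255.

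**3. Split the post-follow-up interval.**

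| Interval | Days | Share of 112 | SAEs reportable if the investigator is informed |
|---|---|---|---|
| Day 253 to 283 | 30 | 30/112 = 27% | all |
| Day 283 to 365 | 365 − 283 = 82 | 82/112 = 73% | fatal or drug-related |
| Total | 365 − 253 = 112 | 100% | |

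**4. The period itself.** Post-Follow-Up closes at the call or an early termination visit. A patient who completed week 36 and has no call has neither, so the period has no defined end. By SAP 4.5.12 this is most patients.

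**5. The denominator, as illustration.** Assume 80 SAF patients per arm (the planned allocation) and a share with a completed call of 5% to 40%. The documents give no figure for that share. One SAE in a patient who had the call prints as 1/80 = 1.25%. Among those whose period is closed by a call it would be 1/4 = 25% (5% of 80 is 4) to 1/32 = 3.1% (40% of 80 is 32). Neither is a sound incidence, because the numerator is restricted too. The spread shows only how little the printed percentage would mean.

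**The case against.** **The row is not explicitly specified.** SAP 5.8.1 asks for the split by period only where it applies. It defines pre-treatment, treatment-emergent and follow-up AEs, the last ending before the week-36 visit, and no post-follow-up class. The relationship table and the combined AE summary cover only treatment and follow-up. This stands: the row is an inference from section 5 and 5.8. However, 5.8 names four segments without exception, and two of the three new SAE tables lack the limit that the third has.

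**The call may never have been a means of collecting SAEs.** A reader might infer that SAEs were solicited at week 52 and that V2.0 removed that. The documents do not support this. Protocol 8.2.3.8 gives the purpose as joint replacement status, and 9.4.2 covers SAEs that a patient reports, without saying that anyone asks. The adverse-event row of the schedule is an arrow whose extent cannot be read in the available text. Late ascertainment therefore looks largely passive even before V2.0.

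**Not everything is filtered by causality.** All SAEs are reportable in the first 30 days after follow-up, and fatal ones throughout. The rule for the call does not say that it displaces the 30-day rule. This also stands.

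**Joint safety is assessed elsewhere.** It rests on adjudicated imaging to week 36 and on joint-replacement listings, and V2.0 openly states that most calls will not be made. This limits the harm considerably, although the listings help only where information was obtained.

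**Conclusion.** The point holds as a minor inconsistency with one practical consequence. The week-52 phrase in SAP 4.5.1 conflicts with protocol 9.4.1, with the reporting limits later in the same SAP section, and with the V2.0 termination. If the two by-period SAE tables follow the four segments, their post-follow-up percentages would rest on passive reporting that is restricted for 82 of 112 nominal days (73%), over a denominator in which most patients have no defined post-follow-up period. That is not an incidence.

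This assumes nominal visit days, patients who complete follow-up, and a reading of 5.8.1 that includes the fourth segment.

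Three stronger readings go too far. The documents do not show that the row will certainly be printed. They do not allow an estimate of the fraction of late SAEs that would be missed, since that needs a causality split they do not give. They give no sign of bias between arms: whether a patient had the call should depend mainly on enrolment date, which randomisation should roughly balance. Efficacy, TEAE and arthropathy analyses are unaffected.

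**What to change.** 1. In SAP 4.5.1, replace the week-52 phrase with text consistent with protocol 9.4.1 and 9.4.2 and with the V2.0 termination: full recording to the end of follow-up, then the limited reporting rules already set out in that section.
2. In SAP 5.8.1, limit by-arm SAE counts and percentages by period, overall and by severity, to the pre-treatment, treatment and follow-up periods. The relationship table already has a limit of this kind.
3. Put SAEs with onset after follow-up in a listing without percentages. Add a note on the restricted reporting and a flag for whether the week-52 call was made.

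The cost is a few lines of SAP text and one listing, with no change to data collection. The small downside is that SAEs in the 30 days after follow-up, when all are still reportable, appear only in the listing.

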#### **4.5.2. Safety Variables (Secondary Study Endpoints)**

The secondary safety endpoints of the study are:

- The incidence of treatment-emergent adverse events (TEAEs) throughout the study duration
- The incidence of imaging abnormalities consistent with accelerated arthropathies as assessed by X-ray and MRI throughout the study duration
- Presence of anti-REGN5069 antibody development throughout the study duration

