##### 4.1.2.2. Secondary Safety Endpoints

The secondary safety endpoints of the study are:

- The incidence of treatment-emergent adverse events (TEAEs) in patients treated with REGN5069 compared to patients treated with placebo throughout the study duration

- The incidence of imaging abnormalities consistent with accelerated arthropathies as assessed by X-ray and MRI in patients treated with REGN5069 compared to patients treated with placebo throughout the study duration
- Presence of anti-REGN5069 antibody development in patients treated with REGN5069 compared to patients treated with placebo throughout the study duration

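### The TEAE endpoint is stated for the whole study, but SAP TEAEs close 28 days after the last dose; separately, the Follow-Up AE class stops short of the week-36 visit day

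*SAP*

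**What the plan says.** **The endpoint.** Protocol 4.1.2.2 gives it as "The incidence of treatment-emergent adverse events (TEAEs) in patients treated with REGN5069 compared to patients treated with placebo throughout the study duration". SAP 4.5.2 shortens this to "The incidence of treatment-emergent adverse events (TEAEs) throughout the study duration".

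**The definition.** In SAP 5.8.1, TEAEs "are defined as AEs that developed or worsened during the Treatment Periods". SAP 5 ends the Treatment Period 28 days after the last dose. Protocol 10.4.4.1 has the same period and equates its end with week 12, but its TEAE sentence can be read as restricting only exacerbations, not new events, to that period. The clear limit is therefore the SAP's.

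**The tables.** SAP 5.8.1 lists TEAE summaries and says: "The focus of adverse event reporting in the clinical study report is on TEAEs". It also lists "All AEs by SOC and PT", "All SAEs, by study period" and this sentence: "Follow-up AEs will be summarized similarly as TEAEs, as well as AEs occurring during Treatment and Follow-up Periods combined". Table 2 in SAP 1.2.4.2 shows all three of these as insertions in Version 2.0. The same section says that version was written after the sponsor had reviewed the week-12 data. No table is linked to the 4.5.2 endpoint.

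**The follow-up boundary.** SAP 5.8.1 counts Follow-Up AEs from the end of the treatment period "but before Week 36 visit". SAP 5 runs the Follow-Up Period to the Week 36 or Early Termination visit, and SAP 4.5.1 collects AEs until the week-36 visit.

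**The concern.** An endpoint that names a defined term inherits that term's window. Here the endpoint's stated window and the term's window differ, so the tables that carry the endpoint's name do not cover the period the endpoint claims. The combined summary does cover it to week 36. With nothing assigned, either result could be reported as the endpoint, and the two incidences would generally differ. The choice would be made by people who have seen the unblinded week-12 summaries.

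The boundary wording is a smaller, separate matter. Four observation periods are defined but only three AE classes, and the last class stops just before the visit at which AE collection ends. An event first dated on that day would be collected but appear in neither the TEAE nor the Follow-Up AE tables.

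**Working it through.** **Inputs.** Doses are given on day 1, week 4 (day 29) and week 8 (day 57), and week 36 is day 253. Visit windows at weeks 4, 8 and 36 are ±7 days (Protocol Table 1). The TEAE period ends at last dose + 28 days (SAP 5).

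**Reproducing the plan's own figure.** 57 + 28 = day 85, which is the nominal week-12 day. This matches Protocol 10.4.4.1.

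**Share of the first-dose-to-week-36 window outside the TEAE definition.** Formula: (week-36 day − last dose day − 28) / week-36 day.

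| Case | Arithmetic | Outside |
|---|---|---|
| Three doses, on schedule | (253 − 85)/253 = 168/253 | 66.4% |
| Week-8 dose 7 days late, week-36 visit 7 days early | (246 − 92)/246 = 154/246 | 62.6% |
| Week-8 dose 7 days early, week-36 visit 7 days late | (260 − 78)/260 = 182/260 | 70.0% |
| Stopped after two doses (29 + 28 = 57) | (253 − 57)/253 = 196/253 | 77.5% |
| Stopped after one dose (1 + 28 = 29) | (253 − 29)/253 = 224/253 | 88.5% |

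Of the 11 scheduled post-baseline contacts up to week 36 (weeks 1, 2, 4, 8, 12, 16, 20, 24, 28, 32, 36), 6 come after week 12.

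**Classing each onset day by the literal SAP 5.8.1 wording** (three doses, on schedule):

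- days 1 to 85: TEAE
- days 86 to 252: Follow-Up AE (167 days)
- day 253: no class

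Day 253 is the only unclassed day from 1 to 253, that is 1 of 168 follow-up days. If the Follow-Up AE class includes the visit day, as the SAP 5 period can be read to do, no day is left over.

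**What still captures the events.** Onsets on days 86 to 252 are in the Follow-Up AE, combined and all-AE summaries. An onset on day 253 is in the all-AE table, and in the combined table if that table follows the SAP 5 periods. The documents give no basis for estimating how many AEs will carry that date.

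**The case against.** The strongest reply is that the endpoint names TEAEs, SAP 5.8.1 lists TEAE tables and puts the report's emphasis on them, so those tables naturally report the endpoint. The safety objective also speaks of patients treated for up to 12 weeks. On this view the repair is to reword the endpoint to the treatment period. That repair is available, and the documents do not rule it out. But the duration phrase is not obviously a slip: SAP 4.5.2 uses it for the imaging and antibody endpoints too, and both are scheduled at week 36. The 12 weeks in the objective describe dosing.

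Three further objections stand:

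- The combined table first appears after the week-12 results, whereas the last dose + 28 days period is already in the protocol and SAP Version 1.0. Replacing the TEAE table with the combined one would be a post-results change of endpoint analysis.
- The endpoint is descriptive, lies outside the H1 to H6 testing, and goes into an abbreviated report for a discontinued indication.
- On the boundary, SAP 5 may already include the visit day, and recorded onset times could place some events before the visit.

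A reader might also infer more than the documents support:

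- *That follow-up AEs go unreported.* They do not; several listed summaries include them.
- *That two thirds of AEs are missed.* The 66% is a share of days, not of events.
- *That week-36 joint findings could be lost.* Imaging is a separate endpoint with its own adjudicated summaries (SAP 4.6 and 5.8.8), which do not use the AE classes.
- *That early terminators have no end to follow-up.* SAP 5 ends it at the Early Termination visit, and SAP 5.8 adopts those periods.
- *That TEAE and Follow-Up AE counts should sum to the combined count.* Patient counts would not sum anyway, because a patient with events in both periods is counted once. Only event totals could be affected.

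**Conclusion.** Both mismatches are in the text, and both are minor. The TEAE tables as defined cover days 1 to 85 of 253 for a fully dosed patient on schedule. They cannot by themselves deliver an endpoint stated for the whole study. Other listed summaries fill the window to week 36 but are unassigned and were added after results were known. The literal Follow-Up AE rule leaves one collected day, the week-36 visit day, out of the follow-up tables.

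This rests on the SAP's TEAE definition rather than the more ambiguous protocol sentence, on taking the word before at face value, and on week 36 as the practical end of AE observation. Protocol 9.4.1 stops AE recording at the end of follow-up, and SAP 2.3 says only a limited number of patients will have had the week-52 call. Measured against the originally planned day 365, the part outside would be (365 − 85)/365 = 280/365, or 76.7%. SAEs after week 36 are outside the three AE classes but have a place in the SAE summary by study period. The documents do not establish that either table is the only correct endpoint analysis.

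**What to change.** 1. In SAP 5.8.1, replace the closing words of the Follow-Up AE definition ("but before Week 36 visit") with: up to and including the Week 36/Early Termination visit. This aligns it with SAP 5.
2. Keep the TEAE definition and table unchanged, and label the table as the on-treatment result (first dose to last dose + 28 days).
3. In SAP 4.5.2 and 5.8.1, state that for this endpoint the combined incidence, from first dose through the Week 36/Early Termination visit, is shown beside the TEAE table. Title each table by its window.
4. In SAP 1.2.4, record that the combined table and its assignment to the endpoint were added after the week-12 results were reviewed.

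The cost is a few sentences and two table titles, with no new data and no new tables. The combined figure will carry more background events in every arm, and its link to the endpoint is post-results. Showing both windows side by side, with the timing stated, avoids having to prefer one.
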